### **15.2 Statistical Analysis**

#### **Analysis of the Primary Endpoint**

Overall survival will be estimated by Kaplan-Meier curves along with 95% confidence bands to provide precision.

### **Secondary and exploratory analysis**

Analysis of secondary endpoints will be primarily descriptive. Progression-free survival will be estimated by Kaplan-Meier curves. Cumulative Incidence will be used to estimate the probability of relapse and acute GVHD, treating non-event death as a competing risk. Likewise, relapse will be treated as a competing risk when estimating the probability of non-relapse mortality. Response and the number of patient in complete remission will be estimated with simple proportions. Summary statistics using frequencies and proportions of patients will be used to assess adverse and severe adverse events and medians, ranges and descriptive plots for immune therapy. The correlation between *TP53* mutation and response will be assessed with a chi-square test or Fisher's exact test depending on expected cell frequencies. Similar statistics will be used for the correlation against clonal dynamics curing and after the course of therapy.

### **Subgroup Analysis**

We will assess subgroup analysis of endpoints by donor type. Overall survival is not assumed to differ by donor type and this trial is not powered to determine differences within subgroups and will therefore be considered exploratory.

### **15.3 Sample Size**

This study is designed as a two-stage phase II trial to estimate OS. Since the goal is to estimate the OS at a long-term time-point (6 months), our design is a generalization of the Simon design. Rather than suspension of the trial for evaluation after stage 1, this design uses an optimal interim analysis for futility without suspension of accrual as proposed by Huang et al. The goal of this design minimizes the expected sample size under the assumed parameters. Our trial assumes that a 6-month OS of 25% is unacceptably low and a 6-month OS of 50% is a rate worthy of further study. Both the null and alternative hypotheses assume that the OS follow an exponential distribution. Given an overall one-sided type I error of 5%, 32 evaluable patients will provide 80% statistical power.

When 14 patients have been enrolled (stage 1), it is expected that the accrual will stop if the 6 month Kaplan-Meier estimate of OS is less than 30.0%. It is not required that the 14th patient be followed for 6 months prior to making a decision of whether to continue the trial. Once the 14th patient has been enrolled, the statistician can calculate survival to determine if it falls below the cut-point. If the trial reaches the end of stage II after 32 evaluable patients, significant clinical activity would require at least a 6 month Kaplan-Meier estimate of OS of 39.2%. The probability of stopping at the interim analysis under the null hypothesis is 63.5% and 10.9% under the alternative hypothesis. The R package 'Optinterim' with functions 'OptimDes' and 'SimDes' were used to create design parameters. Assuming that 5% of enrolled patients are not evaluable, we expect recruitment of 34 patients.

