## 2 Background

Although allo-HCT is a curative treatment approach for AML and MDS, relapse continues to be the primary cause of death after allo-HCT, with post-relapse 1-year overall survival of only about 20%. Currently there is no standard treatment for post-HCT relapse. Commonly practiced approaches include withdrawal of immunosuppressive medications, hypomethylating agents, aggressive chemotherapy, second allo-HCT, targeted therapies, DLI, or a combination of these. We will apply a combination approach as detailed in the following sections:

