## 2.2 HMAs

The use of HMAs before or after DLI is a popular and less toxic approach compared to lymphodepleting chemotherapy before DLI. HMAs increase antigen expression by leukemia cells and may make them more immunogenic, i.e. primed for a robust GvL effect from DLI. A recent retrospective multicenter study by the German Cooperative Transplant Study Group using azacitidine prior to DLI in 154 patients with relapsed AML or MDS after allo-HCT showed that this therapy is well-tolerated and effective, particularly in patients with low disease burden. Overall response was achieved in a third of the patients and overall survival at 2 years was approximately 30%. In another study using azacitidine prior to DLI in 65 patients with relapse after allo-HCT, there was temporary control of leukemia in ~45% of patients, but only 10% achieved a CR^9. Furthermore, pioneer murine studies by [name] have demonstrated that azacitidine mitigates GVHD while preserving GVL by peripheral conversion of alloreactive effector T cells into regulatory T cells, thus mitigating GVHD without sacrificing GVL effect. Azacitidine after DLI was recently tested in a phase 1 study to prevent development of GVHD. Azacitidine was administrated on days 4, 6, 8 and 10 after DLI with dose escalation schedule of 30–75 mg/m^2 in 39 patients with relapsed AML after allo-HCT. None of the patients developed severe acute GVHD.

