## **15 Statistical Considerations**

### **15.1 Objectives and Study Design**

This is a single-arm, open-label, multi-center modified Simon's two-stage phase II trial of a combined modality treatment for relapsed AML and MDS after allo-HCT. The primary endpoint is 6 month OS measured from day 1, cycle 1. We expect a total of 34 enrolled subjects will allow us to obtain 32 evaluable patients.

Patients are considered evaluable if they receive the first dose of decitabine and ruxolitinib. All other patients will be replaced.

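### Does a 95% confidence band beside a one-sided 5% success rule leave the primary conclusion on 6-month survival open?

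*Combined protocol and SAP*

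**What the plan says.** Section 15.1 defines the endpoint: "The primary endpoint is 6 month OS measured from day 1, cycle 1". Section 15.3 sets the hypotheses ("Our trial assumes that a 6-month OS of 25% is unacceptably low", with 50% as the rate worth pursuing) and the operating characteristics: "Given an overall one-sided type I error of 5%, 32 evaluable patients will provide 80% statistical power". It then gives one rule for the end of stage II: "significant clinical activity would require at least a 6 month Kaplan-Meier estimate of OS of 39.2" percent.

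In Section 15.2 the analysis of the primary endpoint is a single sentence: "Overall survival will be estimated by Kaplan-Meier curves along with 95% confidence bands to provide precision". It names no test, variance or transformation, does not say whether the bands are pointwise or simultaneous, and does not refer to the 39.2% cut.

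No source is given for the 25%. The background offers two survival figures without linking either to it. Section 2 cites "post-relapse 1-year overall survival of only about 20" percent. Section 2.2 cites a retrospective azacitidine plus DLI series in which "overall survival at 2 years was approximately 30" percent, with the treatment described as effective "particularly in patients with low disease burden".

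**The concern.** A one-sided 5% test corresponds to a two-sided 90% interval, not a 95% one. A result just above 39.2% could be reported as significant activity beside a 95% interval that still includes 25%, the rate the protocol calls unacceptably low. If the text left open whether the cut or the interval decides, that choice could be made after the data are seen.

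The 25% adds to the unease. Survival cannot rise with time, so 30% at 2 years means at least 30% at 6 months in the azacitidine plus DLI series. Under the exponential model of Section 15.3, 20% at 1 year would mean 44.7% at 6 months, which is above the success cut. A reader could ask whether passing the rule shows anything of interest.

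**Working it through.** **Inputs.** n = 32, null 25%, alternative 50%, one-sided 5%, interim cut 30.0% at the 14th enrolment, final cut 39.2%, exponential survival (all Section 15.3); accrual over about 2 years (Accrual paragraph). Assumption: all 32 patients are followed to 6 months or death, so the Kaplan-Meier estimate is a simple proportion.

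**1. The plan's own figures.** Simulating the two-stage rule (32 patients over 24 months, 20,000 runs):

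| Quantity | Stated | Simulated |
|---|---|---|
| Power at 50% | 80% | 80.6% |
| Type I error at 25% | at most 5% | about 3.0% |
| Interim stop at 25% | 63.5% | 64.0% |
| Interim stop at 50% | 10.9% | 12.9% |

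The design reproduces to within about 2 points, and the type I error is inside its limit.

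**2. Where the cut sits.** SE at 39.2% = sqrt(0.392 x 0.608 / 32) = 0.0863. The one-sided 95% Greenwood lower limit is 0.392 - 1.645 x 0.0863 = 0.250, so the cut is the one-sided 5% boundary on that scale. Since 12/32 = 37.5% fails and 13/32 = 40.6% passes, 13 is the first passing count.

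**3. Lower limits at 13/32.** SE = sqrt(0.40625 x 0.59375 / 32) = 0.0868. For Greenwood, 0.406 - 1.96 x 0.0868 = 0.236 and 0.406 - 1.645 x 0.0868 = 0.263.

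| Method | Two-sided 95% | One-sided 95% (two-sided 90%) |
|---|---|---|
| Greenwood | 23.6% | 26.3% |
| Log-log | 23.8% | 26.4% |
| Exact | 23.7% | 26.0% |
| Logit | 25.3% | 27.5% |
| Wilson | 25.5% | 27.6% |
| Log | 26.7% | 28.6% |

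Three of the six 95% limits fall below 25% and three lie above it. All six one-sided limits exclude 25%. At 14/32 (43.8%) the lowest of the six two-sided 95% limits is 26.4%, so with pointwise intervals the overlap is confined to one count.

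**4. How often 13/32 occurs.** Simulating the stated rule with accrual of 15 a year (30 DLIs x 50%), 200,000 trials per scenario:

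| True 6-month OS | P(success) | P(success at exactly 13/32) |
|---|---|---|
| 25% | 3.1% | 1.7% |
| 40% | 45.7% | 10.9% |
| 50% | 80.1% | 6.2% |

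**5. The 25% null.** If survival is exponential to 12 months, 20% at 1 year gives sqrt(0.20) = 44.7% at 6 months, and 25% at 6 months gives 0.25 x 0.25 = 6.25% at 1 year. At a true 44.7% the rule declares success about 64% of the time. Without the exponential assumption, 20% at 1 year only requires at least 20% at 6 months, and a 25% null meets that. Early deaths faster than exponential would bring the 6-month figure below 44.7%.

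**The case for a change.** The strongest case for a change is that the analysis section never mentions the success rule and leaves the interval method open. At 13/32 the choice of method decides whether the published interval covers 25%, and just over half of all false successes (1.7 of 3.1 percentage points) fall on that count. If bands is read as simultaneous, the overlap widens: assuming Hall-Wellner bands with critical values of 1.26 to 1.36, the lower limits are 16.6-18.4% at 13/32, 19.7-21.5% at 14/32 and 22.9-24.6% at 15/32. A few sentences would settle this at no cost in patients or error rates.

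The arithmetic stands, and so does the remark that the method is unnamed. The inference that the conclusion is open does not. Section 15.3 contains the only decision rule, a fixed cut on the point estimate with its error rate stated. Section 15.2 gives the bands the purpose of showing precision, and nothing in the document makes them a test or a condition for success. Choosing an interval method late could alter how a borderline result looks, but not whether it passes. The false-success share is a fraction of an error already below 5%. The simultaneous reading has no support in the text beyond the word itself, and it too would leave the rule untouched.

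On the null, it is fair to say that a reason for 25% is missing and that the exponential extrapolation is uncomfortable. But the 1-year figure is a general one counted from relapse, while the trial counts from the first day of treatment. The 2-year figure comes from a retrospective series of a different regimen. Neither fixes the 6-month survival of this trial's patients.

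**Conclusion.** No change is needed. The plan as written gives one pre-specified decision, a 6-month Kaplan-Meier estimate of at least 39.2%, and its stated power and type I error are confirmed. A descriptive 95% interval beside a one-sided 5% rule is common practice and not a contradiction. With complete 6-month follow-up and pointwise intervals, the two can look at odds only at 13/32, and then only under some methods. That outcome is a success in about 2%, 11% and 6% of trials at true survival of 25%, 40% and 50%. With censoring, estimates between 39.2% and about 42% would behave in the same way on the Greenwood and log-log scales.

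An analyst would sensibly name the interval method, and could show the two-sided 90% interval beside the decision. A sentence on why 25% was chosen would help readers judge what passing the rule means. These are reporting preferences: no decision, error rate, cut-point or sample size depends on them, and 25% is unexplained but not shown to be wrong.

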### **14.2 Secondary Endpoints**

Secondary endpoints of safety and efficacy are measured as below.

- OS at 12 months
- Cumulative incidence of grade II-IV acute graft-versus-host disease (aGVHD II-IV) at 3 months
- PFS at 6 and 12 months in patients
- Cumulative incidence of relapse at 6 and 12 months
- Complete remission (CR) at 6 and 12 months
- Cumulative incidence of non-relapse mortality (NRM) at 6 and 12 months
- Best response until next line of treatment, death, or last follow up, whichever occurs sooner

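### Is the unsourced 25% six-month null too low for a pass at 39.2% to be read as clinical activity?

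*Combined protocol and SAP*

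**What the plan says.** Section 15.1 defines the endpoint: "The primary endpoint is 6 month OS measured from day 1, cycle 1". Section 15.3 sets the hypotheses. The lower rate is introduced with "Our trial assumes that a 6-month OS of 25% is unacceptably low", and 50% is the rate that would merit further study. The section adds that "Both the null and alternative hypotheses assume that the OS follow an exponential distribution". With one-sided error of 5%, 32 evaluable patients are said to give 80% power. Accrual is expected to stop if the Kaplan-Meier estimate at the 14th enrolment is below 30.0%. At the end, "significant clinical activity would require at least a 6 month Kaplan-Meier estimate of OS of 39.2" percent.

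No source or derivation is given for 25%. The survival figures cited elsewhere are "post-relapse 1-year overall survival of only about 20" percent (Section 2) and, for a retrospective azacitidine-DLI series of 154 patients, "overall survival at 2 years was approximately 30" percent (Section 2.2). Neither is converted to a six-month rate or linked to the null.

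On reporting, Section 15.2 says "Overall survival will be estimated by Kaplan-Meier curves along with 95% confidence bands to provide precision", Section 14.2 lists "OS at 12 months" as a secondary endpoint, and the Accrual paragraph plans a further year of follow-up after the last enrolment.

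**The concern.** In a single-arm trial the null does the work of a control group. If it lies below what existing treatment achieves, the 5% error rate protects against the wrong thing, and a regimen that adds nothing can be declared active.

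The protocol's own figures invite that suspicion. Under an exponential curve, 25% at six months means 6.25% at twelve, well below the cited 20%. Run the other way, 20% at twelve months means 44.7% at six, which is above the 39.2% success cut-off. The azacitidine-DLI figure needs no model: a survival curve cannot rise, so with about 30% alive at two years at least about 30% were alive at six months. That already exceeds the null.

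At stake is whether a positive result could be read as an advance when survival is no better than in the cited literature.

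**Working it through.** **Inputs.** From Section 15.3: null 25%, alternative 50%, stop below 30.0% at 14 enrolled, pass at 39.2% or more with 32 evaluable. From Section 4: 34 patients over 24 months, or 17 a year. From Sections 2 and 2.2: about 20% at one year and about 30% at two years. Assumed: no dropout before six months.

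**The plan's own figures first.** With complete follow-up, 0.392 × 32 = 12.5, so passing means at least 13 of 32 alive at six months. The two-stage rule was simulated with the Kaplan-Meier estimate taken at the 14th enrolment on partial follow-up, exponential survival, accrual of 15 to 17 a year, evenly spaced or Poisson.

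| Quantity | Section 15.3 | Simulated |
|---|---|---|
| Power at 50% | 80% | 79.6–81.0% |
| Pass at 25% | at most 5% | about 3% |
| Interim stop at 25% | 63.5% | 59.7–63.5% |
| Interim stop at 50% | 10.9% | 12.3–13.5% |

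The design does approximately what it says.

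**Pass probability by true six-month OS** (17 a year):

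| True 6-month OS | Pass |
|---|---|
| 20% | 0.5% |
| 25% | 3% |
| 26.5% | just under 5% |
| 27% | just over 5% |
| 30% | 11% |
| 35% | 26% |
| 40% | 46% |
| 45% | 65% |
| 50% | 80% |

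The one-sided 5% limit therefore holds up to a true rate of about 26.5%, not only at 25%.

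**What the one-year figure implies.** For a Weibull curve with shape k and S(12) = 0.20, S(6) = 0.20^(0.5^k).

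- k = 1: 0.20^0.5 = 44.7%; pass about 64%.
- k = 0.75: 0.20^0.595 = 38.4%; pass about 39%.
- k = 0.5: 0.20^0.707 = 32.0%; pass about 16%.
- No model: S(6) is at least 20%; pass 0.5% or more.

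The shapes 0.5 to 1 are assumptions that appear nowhere in the documents, so 16–64% is a sensitivity range. A curve with 25% at six months and 20% at twelve needs the average hazard to fall by a factor of ln(0.25)/ln(0.20/0.25) = 1.386/0.223 = 6.2 after month six. That is steep but not impossible, and the rule then passes about 3% of the time.

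**How reliable the back-extrapolation is.** The same exponential step applied to 30% at two years gives 0.30^(6/24) = 0.30^0.25 = 74% at six months, far above the protocol's own 50% target. A constant hazard carried back through a past cohort is not a safe guide to its early survival.

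**What a marginal pass would show.** With complete follow-up, the exact two-sided 95% lower limit is 23.7% at 13/32 and 31.9% at 16/32. At twelve months, 12/32 alive has lower limit 21.1% and 11/32 has 18.6%.

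**The case for a change.** The best case for a change is that readers will judge a label of clinical activity against the survival the protocol cites, since there is no control arm, and that nothing in Section 15.3 tells them a pass speaks only to rates up to about 26.5%. At the model-free 30% bound the chance of passing is about 11%, roughly twice the nominal 5%. A few sentences would cost nothing in sample size or follow-up, and 12-month OS could be set beside the 20% figure without any assumption about curve shape.

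Part of this stands. The 25% is unsourced, and it is below the one bound the documents supply without a model. But that bound comes from a retrospective, possibly selected series. The 20% figure is survival after relapse in a general population, while trial OS starts at cycle 1 day 1 in patients chosen for donor chimerism, organ function and absence of active GVHD. Neither is a six-month rate for this population, so neither shows that 25% is wrong.

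The proposed additions would also leave every number, cut-off and analysis as it is. Making the 12-month comparison a second condition would be costly: with 50% alive at six months and a true 12-month OS of 30% or 40%, a six-month pass together with a 12-month lower limit above 20% occurs only 22% or 61% of the time. Requiring it before any conclusion would delay the primary result for a comparison that is descriptive at best.

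**Conclusion.** No change follows. Section 15.3 offers 25% as a rate too low to be acceptable, which is an ordinary judgement in a single-arm phase II trial. It does not call 25% historical or say that passing shows superiority to past treatment. Null, alternative, error rate and cut-off stand together in one section, so the test is visible. No stated figure or rule is shown to be wrong, and raising the null would be a trade-off against sample size or power rather than a correction.

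The size of the issue depends on a rate the documents do not give. If background six-month OS is at or below about 26.5%, the 5% error holds; at 30% the rule passes about 11% of the time; the 16–64% range applies only if Weibull shapes of 0.5 to 1 describe past cohorts. These figures assume no dropout before six months and accrual near 17 a year.

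The planned reporting covers the interpretive gap. A bare pass at 13/32 would appear with a lower limit of about 23.7%, which does not exclude even 25% in a two-sided 95% interval, and 12-month OS will be available to set beside the literature. A sentence in Section 15.3 giving the reasoning for 25% would help a reader but is optional.

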## **Accrual**

We perform approximately 30 DLIs per year at the collaborating institutions combined. Considering ~50% screen failures and enrollment on competing trials, we expect to complete enrollment in approximately 2 years with an additional year of follow up after the last patient has been enrolled.

## **15.4 Stopping Rules**

### **Toxicity Monitoring and stopping rules**

Monitoring guidelines are developed to monitor excess toxicity using a continuous monitoring strategy based on an adaptation of Pocock stopping boundaries. In the event that a stopping rule is triggered, enrollment will be halted and reviewed by the full study committee and if appropriate by the IRB, prior to initiation of re-enrollment. Additionally, the FDA will be informed if a stopping rule is triggered. The stopping rule was calculated using the following website: <http://cancer.unc.edu/biostatistics/program/ivanova/ContinuosMonitoringForToxicity.aspx>

### **Grade III-IV aGVHD until 3 months after the last cycle of treatment**

Stopping rules were developed for excessive grade III-IV aGVHD. Previous results from trials of HMA plus DLI have reported an incidence of ~10% for aGVHD III-IV. The goal is to construct a boundary based on aGVHD grade III-IV such that the probability of early stopping is at most 5% if the true rate is equal to 10% and our sample size is 34. Given these parameters, the upper stopping boundary for aGVHD grade III-IV is 2 events out of 2 patients, 3 out of 6, 4 out of 10, 5 out of 15, 6 out of 21, 7 out of 27 or 8 out of 33. The probability of early stopping from excessive aGVHD grade III-IV if the true probability is 30% is 86%.

## **16 Ethical and Regulatory Considerations**

### **16.1 Good Clinical Practice**

The study will be conducted in accordance with the appropriate regulatory requirement(s). Essential clinical documents will be maintained to demonstrate the validity of the study and the integrity of the data collected. Master files should be established at the beginning of the study, maintained for the duration of the study and retained according to the appropriate regulations.

### **16.2 Ethical Considerations**

The study will be conducted in accordance with ethical principles founded in the Declaration of Helsinki. The IRB will review all appropriate study documentation in order to safeguard the rights, safety and well-being of the patients. The study will only be conducted at sites where IRB approval has been obtained. The protocol, informed consent, written information given to the patients, safety updates, annual progress reports, and any revisions to these documents will be provided to the IRB by the investigator.

### **16.3 Informed Consent**

All potential study participants will be given a copy of the IRB-approved consent to review. The investigator or designee will explain all aspects of the study in lay language and answer all questions regarding the study. If the participant decides to participate in the study, he/she will be asked to sign and date the consent document. Patients who refuse to participate or who withdraw from the study will be treated without prejudice.

